NCT04834817 Effect of Combined Red and Near Infrared Light-emitting Diode (LED) Therapy on Tissue Regeneration Post Laser Treatment (Document date: 11/29/2023)

[figure not shown]
STUDY PROTOCOL

Background & Purpose of the Research

The objective of this study is to evaluate the effect of a combination of near infrared (830 nm) red (633 nm) and blue (465nm) light-emitting diode (LED) therapy on wound healing after application of low density ablative fractional laser to bilateral inner biceps, close to the axilla. Our hypothesis is that the LED therapy will result in less post treatment pain and in a faster healing time after ablative fractional laser application.

Literature reveals that light-emitting diodes (LED) promote healing of skin wounds by decreasing inflammation, increasing fibroblast proliferation, stimulating angiogenesis, formation of granulation tissue, and increasing collagen synthesis.1 LED treatment is of interest to the medical community in large part for its safety profile – at 6.5 milliwatts, it emits energy far less than that of a household flashlight. To further determine the extent to which LED promotes healing and to evaluate the relative speed at which it does so compared to other conservative management, this study sets out to assess wound healing with LED treatment after application of fractional ablative laser to the bilateral inner biceps, close to the underarm. Ablative fractional laser treatment results in well-healed regeneration of the superficial layers of the skin, thus an ablative fractional laser with the following parameters will be used to induce a two-inch by two-inch, superficial wound on each ventral bicep: 650 micrometers at 150 J and 5.5% density, similar to parameters used to treat scars. After laser application, we will evaluate the effect of a combination of near infrared (830 nm) red (633 nm) and blue (465nm) light-emitting diode (LED) therapy on wound healing post laser treatment. Product under investigation: BioPhotas Celluma LED device Technical parameters Red: 640nm+/-25nm NIR: 880nm+/-50nm Blue 465nm Irradiance 6.5 mW/cm2 Fluence 11.7J/cm2

Literature reveals that light-emitting diodes (LED) promotes healing of skin wounds by decreasing inflammation, increasing fibroblast proliferation, stimulating angiogenesis, formation of granulation tissue, and increasing collagen synthesis. One proposed mechanism for these changes called the Karu Model is shown below (Figure 1):

Source: Huang YY, et al. 2009.

Many studies have demonstrated these effects on wound healing in vitro, as below, where "LLLT" refers to low-level light therapy. See Figures 2 & 3 below.

[figure not shown]
[figure not shown]

Fig. 3 LLLT increases *in vitro* wound healing in A549, PtK2, and U2OS using wavelengths 806 and 901 nm. (a and b) Cells were treated and evaluated as in (Fig. 2), but treated with LLLT 806 or 901 nm and wound healing was measured after 24 h. The green area marks the wound, bar, 100 μ m. Data represent the mean \pm SEM of at least three separate experiments with N=12; ****p<0.0001, *p<0.05 compared with control or for the indicated comparison.

Spitler and Berns: Comparison of laser and diode sources for acceleration of in vitro wound healing...

Nasa has demonstrated reproducible results here. See Figure 4, 6, and 7.

[figure not shown]

FIG. 4. LED response at 4 J/cm², 50 mW/cm² using individual wavelengths of 670, 728, and 880 nm (percentage change from control versus number of hours after LED treatment).

[figure not shown]

FIG. 6. HaCAT epithelial cell collagen synthesis at 8 J/cm², 50 mW/cm², 670 nm. Shown in 24-h ³H proline incorporation.

[figure not shown]

FIG. 7. Change in wound size in rat ischemic wound model versus time (days).

[figure not shown]
There is also evidence that LED treatment post-sternotomy leads to a decrease in bleeding and dehiscence, while providing an analgesic effect.

Visible LED light treatment at various wavelengths have been shown to not only increase growth in multiple cell lines but also to accelerate wound healing in human studies for skin grafts, chronic leg ulcers, and post-CO2 laser treatment.

Further study on the mechanism by which LLLT induces these changes suggests that LED causes changes in mitochondrial complexes I, II, III, IV, succinate dehydrogenase, and cytochrome C (part of complex IV) ultimately leading to increased nitric oxide (NO) and thus increased wound healing.

Given these past results, we now want to confirm response in human subjects.

Spitler and Berns: Comparison of laser and diode sources for acceleration of in vitro wound healing...

The primary endpoint of this study is time in days to complete healing of the treatment sites. Clinical grading shall be by blinded assessment, using recognized assessment techniques. A secondary outcome measure will be post-treatment pain on a 10-point scale.

Relevant references/articles to support the rationale for the research:

Appropriate eye protection in the form of dedicated laser goggles will be provided to the patient and all other individuals in the treatment room. Ablative fractional laser treatment test area will be (5.5% density/700um) delivered to both inner biceps, close to the underarm to an approximately 3 x 3 cm square area. Subjects will evaluate pain and discomfort immediately after the treatment using an 11-point Visual analogue scale. Clinical digital photography of test and control site post induction will be recorded. Immediately after photography the test area will be irradiated with the Biophotas Celluma for 30 minutes. The Celluma light panel will be disinfected prior to every use over open wound. The Control side will be untreated. The Celluma POD device will not be used over known cancer tumor or metastasis.

30 minutes after treatment with the Biophotas Celluma subjects will evaluate pain and discomfort for test and control sites using an 11-point Visual analogue scale.

Days 1-27 – treatment with Celluma

Test site will receive a 30-minute treatment of Celluma, 3 treatments per week for 4 weeks, with the first treatment being day 0 immediately after ablative fractional laser treatment test area. Day 1, 3, 6 subjects will record daily site symptoms including pain and discomfort and complete a treatment log in a patient diary.

Days 2*, 4*, 6*, 9, 13, 20, and 27 – Assessments

* Scheduled follow-up visits may be adjusted 1-2 days based on clinic or patient availability.

Clinical digital photography of test and control site will be recorded. Investigator assessment of treatment response using visual analogue scales to include Time to heal, Percentage healing, edema, erythema, swelling and crusting.

Subject assessment of treatment response using a grading of response.

Day 34 – Assessments Clinical digital photography of test and control site will be recorded. Investigator assessment of treatment response using visual analogue scales to include Time to heal, Percentage healing, edema, erythema, swelling and crusting.

Subject assessment of treatment response using a grading of response.

Day 55 – Final follow up

Clinical digital photography of test and control site will be recorded.

Investigator assessment of treatment response using visual analogue scales to include Time to heal, Percentage healing, edema, erythema, swelling, crusting, discoloration, and scarring

Subject assessment of treatment response using a grading of response.

If either or both skin wounds have not completely healed by this time, an additional follow-up visit will be scheduled at day 62 (one week after original final follow-up visit).

Study Narrative and Baseline Day 0

- 1. After completing informed consent and photography release forms subjects will be enrolled into the study.
- 2. Subjects will be randomized to which arm denotes the test or control side.
- 3. The clinical investigator will assess baseline characteristics including assessment of Fitzpatrick skin type, ethnicity, demographics and general medical history and status, and concomitant medications.
- 4. Subjects will be instructed on the use of the Biophotas Celluma LED device and observed switching the device ON/OFF, positioning the device and after treatment care of the device.
- 5. Clinical digital photography of treatment site will be recorded immediately prior to treatment
- 6. Ablative fractional laser treatment test area (5.5% density/700um) will be delivered to both inner biceps, close to the underarm an approximately 3×3 cm sq area.
- 7. Immediately after the test area administration, subjects will evaluate pain and discomfort using an 11- point Visual analogue scale.
- 8. Clinical digital photography of test and control site post induction will be recorded.
- 9. Immediately after photography the test wound will be irradiated with the Biophotas Celluma for 30 minutes. The Control side will be untreated. Subjects will be observed self-administrating the treatment.
- 10. 30 minutes after treatment with the Biophotas Celluma subjects will evaluate pain and discomfort for test and control sites using an 11-point Visual analogue scale.
- 11. Subjects will be instructed to treat the test site daily for 28 days and to complete their treatment log and diaries daily. Subjects will be given contact details for any adverse incidents or questions they may have.
- 12. Subjects will be given a date and time to return to the clinic for assessment.

Days 1-27

- 1. Subjects will complete their diaries and treatment log daily.
- 2. Daily, immediately before and 30 minutes after each Biophotas Celluma treatment the subject will record pain and discomfort.
- 3. From Day 2-27 subjects will record itching immediately before and 30 minutes after each Biophotas Celluma treatment.

Days 2*, 4*, 6*, 9, 13, 20 and 27 - Assessments

- 1. Subjects will return to the clinic on days 2, 4, 6, 9, 13, 20 and 27. * Scheduled follow-up visits may be adjusted 1-2 days based on clinic or patient availability.
- 2. The subject will be questioned generally to ascertain any changes in health or concomitant medication.
- 3. The subject's diary will be reviewed, and the subject will be questioned to ascertain any potential adverse incidents.
- 4. Clinical digital photography of test and control site will be recorded.
- 5. The Investigator will assess both test and control sites using visual analogue scales to include time to heal, percentage healing, edema, erythema, swelling and crusting.
- 6. Subject will assess treatment response using a grading of response.
- 7. The subject will be given a date and time to return to the clinic for the next assessment.

Day 34

- 1. The subject will be questioned generally to ascertain any changes in health or concomitant medication.
- 2. Clinical digital photography of test and control site will be recorded.
- 3. The Investigator will assess both test and control sites using visual analogue scales to include time to heal, percentage healing, edema, erythema, swelling and crusting.
- 4. Subject will assess treatment response using a grading of response.
- 5. The subject will be given a date and time to return to the clinic for the last assessment.

Day 55

- 1. The subject will be questioned generally to ascertain any changes in health or concomitant medication.
- 2. Clinical digital photography of test and control site will be recorded.
- 3. The Investigator will assess both test and control sites using visual analogue scales to include time to heal, percentage healing, edema, erythema, swelling and crusting.
- 4. Subject will assess treatment response using a grading of response. If there are no continuing adverse events and the patient has completed all diaries, they will be allowed to keep the Celluma device, and signed off the study.

Digital photographs will be taken of each ventral arm from antecubital fossa to axilla before laser application, directly after laser application, and at designated assessment visits in clinic. The photos will only include the ventral arm in the frame. If there are tattoos present in the area they will be covered using a black photography cloth or blue medical drape.

Subject will be asked to give consent prior to participating in the study by signing an informed consent form and photography release form.

Publications and/or presentations that result from this study will not include subject identifiable information.

Time in study 56 days from Baseline visit (day 0)

Study Design

This is a single-center, randomized single-control study. One arm will serve as control and will not receive Celluma LED device treatment. The laterality of the control and test arms will be randomized.

Methods of evaluation

- 1. Fitzpatrick skin typing at baseline including ethnicity
- 2. General medical history and concomitant medications
- 3. Standardized clinical photography
- 4. Investigator assessment of treatment response using applicable scales to include:
 - i. Time to heal
 - ii. Percentage healing
 - iii. Edema iv. Erythema
 - iv. Crusting
 - v. Discoloration
 - vi. Scarring
- 5. Subject assessment of pain, discomfort, and itching post treatment
- 6. Patient diaries
- 7. Adverse event recording

Methods of assessment

Authors note:

Scales used to describe healing in leg ulcers and general or surgical wounds, apart from the Leg Ulcer Measurement Tool LUMT, lack comprehensive and quality evaluation with respect to validity, reliability, and sensitivity. The author has reviewed the Food and Drug Administration's guidelines on wound healing and has identified the following areas that constitute important measurement metrics in wound healing.

Clinical assessment

Clinical photography

Digital clinical photography shall be taken at baseline, immediately post treatment and at each assessment point.

Healing assessment

Clinical assessment shall be performed by independent and blinded assessors, based on visual examination and clinical photography of the test and control areas at baseline (before the first session), and at each assessment point.

Healing shall be graded at each assessment on a 5-point visual analogue scale as follows:

i. Excellent: 81% - 100% healing
ii. Very Good: 61% - 80% healing
iii. Good: 41% - 60% healing
iv. Fair: 21% - 40% healing
v. Little or no change: 0% - 20% healing

Erythema

Clinical assessment shall be performed by independent blinded assessors, based on visual examination and clinical photography of the test and control areas at baseline (before the first session), and at each assessment point.

Erythema shall be graded at each assessment on an 11-point scale as follows:

- i. Little to No Erythema
- 0
- 1

ii. Mild Erythema

- 2
- 3
- 4
- iii. Moderate Erythema
- 5
- 6
- 7

iv. Severe Erythema

- 8
- 9
- 10

Swelling

Clinical assessment shall be performed by independent and blinded assessors, based on visual examination and clinical photography of the test and control areas at baseline (before the first session), and at each assessment point.

Swelling shall be graded at each assessment on a 11-point scale as follows:

- i. No Swelling evident
- 0
- 1
- ii. Mild Swelling
- 2
- 3
- 4
- iii. Moderate Swelling

- 5
- 6
- 7

iv. Severe Swelling

- 8
- 9
- 10

Crusting

Clinical assessment shall be performed by independent and blinded assessors, based on visual examination and clinical photography of the test and control areas at baseline (before the first session), and at each assessment point.

Crusting shall be graded at each assessment on a 11-point visual analogue scale as follows:

- i. No crusting evident
- 0
- 1

ii. Mild Crusting

- 2
- 3
- 4

iii. Moderate Crusting

- 5
- 6
- 7

iv. Severe Crusting

- 8
- 9
- 10

Subject assessment

Pain

Pain shall be assessed using an 11-point Visual Analogue Scale (VAS) (0-10-point scale). The Scale will be used at the following timepoints.

- i. Immediately after the test area performance
- ii. 30 minutes after the first treatment session of Biophotas Celluma.
- iii. Daily, immediately before and 30 minutes after each Biophotas Celluma treatment.

Discomfort

Discomfort shall be assessed using an 11-point Visual Analogue Scale (VAS) (0-10-point scale). The Scale will be used at the following timepoints.

- i. Immediately after the test area performance
- ii. 30 minutes after the first treatment session of Biophotas Celluma
- iii. Daily, immediately before and 30 minutes after each Biophotas Celluma treatment

Itching

Itching shall be assessed using an 11-point Visual Analogue Scale (VAS) (0-10-point scale). The Scale will be used at the following timepoints.

Daily, immediately before and 30 minutes after each Biophotas Celluma treatment.

STATISTICAL ANALYSIS PLAN

The primary endpoint measured in the study is length of days to reach either a 0 or 1 on the 11-point scale for erythema, swelling, and crusting, as well as 80-100% overall healing on the treatment arm compared to the control arm. Comparisons of pain, discomfort, and itch ratings will also be made between treatment and control arms by calculating the average scores.

Times to full healing and times to resolution of all side effects will be described by frequency distributions together with mean values and associated 95% confidence limits.

A comparable study of LED therapy involving 10 patients gave mean (SD) treated healing time of 13.5 (1.1) days and mean (SD) untreated healing time of 26.8 (1.6) days. Mean (SD) of relative reduction in healing time was 50% (2.2%) and the lowest relative reduction was 48%. Assuming similar results for the proposed study, the study size of 25 would virtually guarantee statistically significant reductions in healing time. Based on 95% confidence intervals, the mean treated healing time, mean untreated healing time and mean relative reduction in healing time will be estimated with precisions of 3.1%, 2.3% and 1.7%.

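### Time to healing is to be summarised by a plain mean, with no rule for sites that have not met the endpoint at their last visit

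*Combined protocol and SAP*

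**What the plan says.** **Follow-up.** Under Research Procedures, the day 55 visit is the final one, with one contingency: "If either or both skin wounds have not completely healed by this time, an additional follow-up visit will be scheduled at day 62". No later visit is described. The Study Narrative signs a subject off at day 55 on adverse events and diaries, without mentioning healing status. The time in study, given just before Study Design, is 56 days.

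**Endpoint.** The SAP counts the "length of days to reach either a 0 or 1 on the 11-point scale for erythema, swelling, and crusting", together with at least 80% overall healing.

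**Analysis.** "Times to full healing and times to resolution of all side effects will be described by frequency distributions together with mean values" and 95% confidence limits. No test is named. There is no censoring rule, missing-data rule, dropout allowance or survival method.

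**Planning figures.** The last paragraph of the SAP takes from a 10-patient study a "mean (SD) treated healing time of 13.5 (1.1) days" and a "mean (SD) untreated healing time of 26.8 (1.6) days". It concludes that "the study size of 25 would virtually guarantee statistically significant reductions in healing time".

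**The concern.** The primary endpoint is a time to event that needs four conditions to hold together. For a site that misses any of them at its last visit, the healing time is known only to exceed that visit. A plain mean has no place for such a value. The analyst would have to drop the site or enter a day on which it did not heal, and either choice understates healing time. Because slow sites are the likelier ones to be unobserved, this can happen even when dropout is unrelated to healing. If the untreated side heals more slowly, as hypothesised, it loses more values and the estimated benefit tends to shrink.

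The day-62 visit does not close the gap, because its trigger (complete healing) is not the SAP endpoint. A site judged completely healed at day 55 but scoring 2 or more for erythema has no endpoint value and gets no further visit. Conversely, a site at 85% healing with all scores at 0 or 1 has met the endpoint but is still sent to day 62.

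**Working it through.** **1. Inputs from the SAP.** n = 25 subjects, each with a test and a control site; treated 13.5 (SD 1.1) days; untreated 26.8 (1.6) days; relative reduction 50% (2.2%); precision "Based on 95% confidence intervals".

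**2. The plan's own figures.** Relative half-width = 1.96 × SD / √25 / mean:
- treated: 1.96 × 1.1 / 5 = 0.431; / 13.5 = 3.19%
- untreated: 1.96 × 1.6 / 5 = 0.627; / 26.8 = 2.34%
- relative reduction: 1.96 × 2.2 / 5 = 0.862; / 50 = 1.72%

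These match the stated 3.1%, 2.3% and 1.7% when cut to one decimal, and they assume that all 25 values are observed. The power statement also holds. The SD of the paired difference is at most 1.1 + 1.6 = 2.7, so 13.3 / (2.7 / 5) = 24.6 standard errors.

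**3. Unhealed sites under those figures.** Day 55 lies (55 − 26.8) / 1.6 = 17.6 SD above the untreated mean, and day 62 lies (62 − 26.8) / 1.6 = 22 SD above it. The normal tail probabilities are about 10⁻⁶⁹ and 10⁻¹⁰⁷. The mean of healed sites and the restricted mean to day 62 are both 26.8 days.

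**4. What would make it matter.** With the mean kept at 26.8 and a normal distribution, 1% unhealed at day 62 needs an SD of 35.2 / 2.326 = 15.1 days, and 5% needs 35.2 / 1.645 = 21.4 days.

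**5. Dropping sites unhealed at day 62.** Assumed: lognormal times with mean m and coefficient of variation CV. Then σ² = ln(1 + CV²), μ = ln m − σ²/2 and P = Φ((ln 62 − μ)/σ). The mean of healed sites is m·Φ((ln 62 − μ − σ²)/σ)/P. The restricted mean is P × that mean + (1 − P) × 62.

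| Assumed mean, CV | Unhealed at day 62 | Mean of healed sites | Bias | Restricted mean |
|---|---|---|---|---|
| 26.8, 30% | 0.1% | 26.75 | −0.05 | 26.79 |
| 26.8, 50% | 2.2% | 25.71 | −1.09 | 26.51 |
| 40, 30% | 5.1% | 38.37 | −1.63 | 39.57 |
| 40, 50% | 12.2% | 34.42 | −5.58 | 37.79 |

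**6. Adding early loss.** Simulation with an assumed 10% or 20% of subjects lost uniformly over days 0-55, the two sites independent, and sites without a value dropped:
- Plan's means and SDs: 2-5% of treated and 5-10% of control sites have no value. The difference reads 13.30 and 13.29, against a true 13.3.
- Plan's means, CV 50%: 12.06 and 11.89 instead of 13.3 (complete pairs only: 12.02 and 11.81).
- Means 20 and 40, CV 50%: 14.53 and 14.38 instead of 20.

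In the second case most of the shortfall comes from the day-62 limit rather than from dropout. With no dropout the difference is already 25.71 − 13.48 = 12.23.

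**The case against.** The strongest defence is that the plan's figures leave nothing to censor. Step 3 bears this out, so a reader who infers that the plan expects unhealed sites, or that its means are biased, goes further than the documents do. The day-62 sentence is conditional. What remains is that the figures come from one study of 10 patients, described only as comparable and not said to have used this composite endpoint, while the sponsor still schedules visits at days 34, 55 and possibly 62.

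Other tempting readings also fail:
- **That the bias would swamp the planned precision.** With 25 control sites, the rest at an assumed 30 days and 1, 2 or 3 at day 62, dropping the latter moves the mean by 1.28, 2.56 or 3.84 days, against 2.34% of 26.8 = 0.6 days. But that 0.6 rests on an SD of 1.6, under which no site reaches day 62. The example's own SDs are 6.4, 8.9 and 10.6, giving half-widths of 2.5, 3.5 and 4.2 days, which the shifts do not exceed.
- **That the plan will drop such sites.** It is silent. If day 62 were entered instead and nobody were lost earlier, the result would equal the restricted mean to day 62. The error would then lie in presenting it as an unrestricted mean.
- **That a day-62 visit shows a missing primary value.** The site may already have met the SAP endpoint.
- **That anyone leaving early has no healing time.** Only loss before healing matters.
- **That the LED effect would be inflated.** In the scenarios run, the bias goes against it.

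The planned frequency distribution could show unhealed sites as a category, but the plan does not say so, and that would not repair the mean.

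**Conclusion.** The point holds in a conditional form. The plan foresees unhealed sites, but its only stated summary of the primary endpoint cannot use them. Under its own planning figures the effect is nil for practical purposes: about 0.01 day in the difference, even with 20% dropout. If healing is far more variable or slower than assumed, dropping such sites understates the benefit, by roughly 1.2 to 1.4 days out of 13.3 at CV 50% and by about 5.5 days out of 20 with means of 20 and 40. The CVs, slower means, dropout rates and lognormal shape are assumptions; the documents give none of them. This is an inexpensive safeguard for the primary result and does not show that the result will be wrong.

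**What to change.** In the SAP:
- Treat a site that has not met the SAP endpoint at its last visit as right-censored there, and report the number unhealed per arm.
- Report Kaplan-Meier (or interval-censored) medians per arm and a restricted mean to a fixed day, labelled as restricted.
- Compare arms within subject by a sign or signed-rank test. An unhealed site ranks slower than its healed partner, and pairs unhealed on both sides count as ties. Both sites share the same last visit, so this order is known even after early loss. The sign test needs no more than that; a signed-rank test also needs a rule for ranking the size of differences that involve a censored site.
- Reconcile the trigger for the day-62 visit, the day-55 sign-off and the 56-day time in study with the SAP endpoint, so that it is clear when observation of a site ends.

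The cost is SAP wording and slightly more analysis. The small downside is that the effect is reported as a median or restricted mean and not as a simple mean. If the planning figures hold, nothing is lost, since the restricted mean to day 62 is then also 26.8 days.

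### The post-laser, pre-LED pain and discomfort score has no baseline role in the SAP and is not required per site, which costs precision and leaves any laser difference between sides unadjusted

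*Combined protocol and SAP*

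**What the plan says.** Study Narrative and Baseline Day 0 puts randomization of side at item 2, the laser at item 6, a pain and discomfort score at item 7, photography at item 8 and the first LED session at item 9. Item 7 reads: "Immediately after the test area administration, subjects will evaluate pain and discomfort", on an 11-point scale. The next score, item 10, names both sites: "30 minutes after treatment with the Biophotas Celluma subjects will evaluate pain and discomfort for test and control sites using an 11-point Visual analogue scale". The Day 0 text under Research Procedures shows the same order and the same contrast.

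Under Subject assessment, the Pain and Discomfort lists both open with the item 7 reading ("Immediately after the test area performance") as timepoint i. The reading 30 minutes after the first session follows, and then the diary readings: "Daily, immediately before and 30 minutes after each Biophotas Celluma treatment". None is labelled a baseline. By contrast, the healing, erythema, swelling and crusting scales each name a baseline before the first session.

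The SAP's whole plan for these outcomes is one sentence: "Comparisons of pain, discomfort, and itch ratings will also be made between treatment and control arms by calculating the average scores". It names no timepoints, change score or covariate. On allocation, Study Design says: "The laterality of the control and test arms will be randomized". Background & Purpose makes less pain one half of the hypothesis and names pain as a secondary outcome.

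**The concern.** The item 7 score is a true pre-treatment value, taken when both wounds exist and neither has had LED. It is the natural covariate for later pain and is already scheduled. The plan does not use it that way, and three things follow.

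- **Precision.** If one wound starts out more painful than the other, that difference stays in the later comparison as noise that could have been removed.
- **Protection.** Side is allocated before the laser is applied, and no concealment from the laser operator is stated. If delivery differed by allocated side, the planned comparison could not correct for it.
- **Dilution.** If the undefined average pools every listed timepoint, a reading that LED cannot have changed enters the outcome.

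Item 7 also leaves open whether each wound gets its own score. If a single overall score is taken, adjustment is impossible, and the missing value cannot be recovered after Day 0.

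**Working it through.** **The plan's own figures.** The SAP's only precision figures concern healing time. With 1.96 × SD / √25 / mean:

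- treated: 1.96 × 1.1 / 5 / 13.5 = 3.19% (stated 3.1%)
- untreated: 1.96 × 1.6 / 5 / 26.8 = 2.34% (stated 2.3%)
- relative reduction: 1.96 × 2.2 / 5 / 50 = 1.72% (stated 1.7%)

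They reproduce, up to truncation, but do not bear on pain or discomfort. The documents give no SD or correlation for those outcomes.

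**Dilution, if all listed readings are pooled.** With t LED sessions there is one pre-LED reading, one after the first session, and two for each later session: R = 2 + 2(t − 1). A constant LED effect is multiplied by 1 − 1/R.

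| Basis | t | R | Loss, 1/R |
|---|---|---|---|
| Daily for 28 days (Study Narrative, item 11) | 28 | 56 | 1.8% |
| Three per week for 4 weeks (Research Procedures) | 12 | 24 | 4.2% |
| Readings on Days 0, 1, 3 and 6 only (Research Procedures diary days) | 4 | 8 | 12.5% |

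The loss depends on the session schedule and diary days. The two sections contradict each other on these and must be reconciled.

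**Precision.** Inputs: n = 25 (SAP) and ρ, an assumed correlation between a subject's pre-LED and post-LED test-minus-control differences. If side has no systematic effect on the laser, and the slope is estimated from normally distributed pre-LED differences, the ratio of adjusted to unadjusted variance is (1 − ρ²)(1 + 1/(n − 3)) = (1 − ρ²)(1 + 1/22).

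| Assumed ρ | Variance factor | Change | Equivalent sample size |
|---|---|---|---|
| 0 | 1.00 × 1.045 = 1.045 | +5% | loss |
| 0.3 | 0.91 × 1.045 = 0.951 | −5% | 1/0.951 = 1.05 (5% more) |
| 0.5 | 0.75 × 1.045 = 0.784 | −22% | 1/0.784 = 1.28 (28% more) |
| 0.7 | 0.51 × 1.045 = 0.533 | −47% | 1/0.533 = 1.88 (88% more) |

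Break-even is at ρ² = 1/23, or ρ of about 0.21. A simulation of 20,000 trials agrees: the SD of the estimate falls from 0.20 to 0.195, 0.177 and 0.146 for ρ of 0.3, 0.5 and 0.7, and (0.195/0.20)² = 0.951, for example.

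**Bias.** The same simulation set the true LED effect to zero and the SD of the pre-LED difference to 1, and varied the mean pre-LED difference. Later differences depended on the laser only through the pre-LED difference. A two-sided 5% test gave these type I error rates:

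| Mean pre-LED difference | Unadjusted, ρ = 0.3 / 0.5 / 0.7 | Adjusted |
|---|---|---|
| 0 (laser unrelated to allocation) | about 5% throughout | about 5% |
| 0.5 SD (laser differs by allocated side) | 11% / 23% / 39% | about 5% |

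In the second row the unadjusted bias is ρ × 0.5 = 0.15, 0.25 or 0.35 SD. With adjustment it is about zero.

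**The case against.** A reader might infer that differences caused by the laser are counted as LED effect. The documents do not support this. Side is randomized, so chance differences between wounds average to zero and the standard error covers them. The first row of the bias table shows this. Bias needs laser delivery that depends on the allocated side. The documents leave that possible but do not indicate that it happens.

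A reader might also infer that the pre-LED score certainly enters the outcome. The SAP does not say so. Its average may be over time within a subject or over subjects at each timepoint, and the timepoint lists can be read as a collection schedule. Under the per-timepoint reading nothing is diluted. Halving of the effect would require averaging the two Day 0 readings alone, and no such analysis is planned.

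On efficiency, the large-sample factor 1 − ρ² would overstate the gain with 25 subjects. Pairing has already removed each subject's general pain level and both sites get the same laser settings, so ρ could lie below 0.3, where there is little or nothing to gain.

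The wording on sites is ambiguous. Item 6 uses one term for the area lasered on both arms, so item 7 may intend two scores. If it yields only one overall score, that score cannot carry wound-to-wound differences into the arm comparison.

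These points limit the size of the concern. They do not remove the basic fact that a scheduled pre-treatment value has no analytic role and is not assured per site.

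**Conclusion.** The point stands as a low-cost improvement to a secondary analysis. The plan collects a pre-LED pain and discomfort score, lists it with the outcome readings, gives it no baseline role and does not require it for each site. With randomized side, the planned comparison is not biased on that account.

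The certain omission is in the specification. The numerical consequences are conditional:

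- Dilution of 1.8% to 12.5% arises only if all listed readings are pooled and the LED effect is constant.
- The variance change of about +5% to −47% rests on an assumed ρ of 0 to 0.7, a range the documents neither give nor exclude.
- The error rates of 11% to 39% require a systematic laser difference of 0.5 SD by allocated side, which is hypothetical. The full correction by adjustment also assumes that the pre-LED score captures that difference.

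The primary endpoint does not use pain or discomfort, and itching has no pre-LED reading. Neither is affected.

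**What to change.** 1. In item 7, the matching Day 0 text under Research Procedures, and timepoint i of the Pain and Discomfort lists, require a separate score for the test site and the control site.
2. In the SAP, exclude this reading from the average and define that average as post-LED readings only.
3. In the SAP, regress each subject's post-LED test-minus-control difference in pain on that subject's pre-LED test-minus-control difference, and do the same for discomfort. Leave the covariate uncentred, so that the intercept estimates the LED effect for wounds that start out equally painful.

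The cost is a phrase on the Day 0 form and a short SAP addition, with no extra visit or procedure. The analysis uses one degree of freedom (23 left instead of 24) and loses a little precision if ρ is near zero, about 5% in variance at ρ = 0.
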